7.2.2 Pharmacokinetics

7.2.2.1 Blood sample schedule

Study drug will be taken QD at cycle1 day 1 and twice daily from the second day of cycle 1 in the first 3 patients. First dose in clinic on days when PK sampling occurs i.e., Cycle 1 Day 1 and Cycle 1 Day15, remaining doses on all other days to be self-administered by patient.

In order to detect PK of a single administration, for the first 3 patients, a single administration will be given on the first day, administration twice daily from the second day. Patients will undergo serial blood sampling 2ml for PK analysis during cycle 1 on day 1 at pre-dose and 15min, 30min, 1, 2, 3, 4, 6, 8 hours post-dose, and 12 hours post-dose (if available); on day 2 at pre-dose; on cycle1 day 7 (pre-dose), cycle1 day 10 (pre-dose), day 15 at pre-dose and 15min, 30min, 1, 2, 3, 4, 6, and 8 hours post-dose, and 12 hours post dose (if available); and day 16 at pre-dose. On day 22, prior to dose administration, a final blood sample was collected for pharmacokinetic analyses. See [Table 7-2](#), [错误!未找到引用源。3](#).

Serial blood samples will be collected from all patients to assess single dose and multiple dose plasma PK of HH2710 and its metabolite. PK parameters will be derived from each individual plasma concentration-time profiles. Refer to [Section 10.6.4](#) for list of PK parameters that will be estimated.

PK blood sample collection and handling

Blood samples will be taken by either direct venipuncture or an indwelling cannula inserted in a forearm vein. At specified time points described in [Table 7-2](#) and [错误!未找到引用源。3](#), 2 mL blood draws will be collected into tubes containing K2 EDTA and gently inverted several times to thoroughly mix the anticoagulant. Tubes will be centrifuged to separate plasma and plasma will

immediately be transferred into labeled 2 mL polypropylene screw-cap tubes. Plasma samples will be placed in a freezer in an upright position until shipment to the bioanalytical laboratory for analysis.

All sampling is relative to the ingestion of HH2710. On days and time points where blood PD samples are to be drawn, the PK sample must be drawn first. The exact collection date and time of all samples must be documented on the PK blood collection CRF pages. The date and exact time of dosing, as well as the date and actual time of blood sampling must be recorded on the CRF.

Refer to the [HH2710-G101 Laboratory Manual] for detailed instructions for the collection, handling, and shipment of PK samples.

Intensive PK sampling will be done in the dose escalation portion of the trial. Additional PK sampling will be drawn every two cycles prior to Day 1 dosing in all patients in the dose escalation between Cycle 1 to Cycle 9 (e.g. Cycle 3 Day 1, Cycle 5 Day 1, Cycle 7 Day 1, Cycle 9 Day 1) ([Table 7-2](#)).

PK samples at pre-dose, 2h, 4h, a 6h, 8h, and 24h post dose will also be obtained at Cycle 1 Day 1 and Cycle 1 Day 15 for patients in the Phase I dose expansion stage and Phase II portions of the trial ([Table 7-3](#)).

Table 7-2: PK blood sampling time for Phase I dose escalation stage

CxDx	C1D1	C1D1	C1D1	C1D1	C1D1	C1D1	C1D1	C1D1	C1D1	C1D2	C1D7	C1D10	C1D15	C1D15	
No.	1	2	3	4	5	6	7	8	9	10	11	12	13	14	15
Time	pre-dose	15min	30min	1h	2h	3h	4h	6h	8h	12h (If available)	24h (pre-dose)	pre-dose	pre-dose	pre-dose	15min
Window (min)	-30	±5	±5	±5	±10	±10	±10	±30	±30	±60	-30	-30	-30	-30	±5
Blood Sampling	2mL	2mL	2mL	2mL	2mL	2mL	2mL	2mL	2mL	2mL	2mL	2mL	2mL	2mL	2mL
CxDx	C1D15	C1D15	C1D15	C1D15	C1D15	C1D15	C1D15	C1D15	C1D16	C2D1	C3D1	C5D1	C7D1	C9D1	NA
No.	16	17	18	19	20	21	22	23	24	25	26	27	28	29	NA
Time	30min	1h	2h	3h	4h	6h	8h	12h (If available)	pre-dose	pre-dose	pre-dose	pre-dose	pre-dose	pre-dose	NA
Window(min)	±5	±5	±10	±10	±10	±30	±30	±60	-30	-30	-30	-30	-30	-30	NA

Blood Sampling	2mL	NA											
----------------	-----	-----	-----	-----	-----	-----	-----	-----	-----	-----	-----	-----	----

Table 7-3: PK blood sampling time for Phase I dose expansion stage and Phase II

CxDx	C1D1	C1D1	C1D1	C1D1	C1D1	C1D2	C1D15	C1D15	C1D15	C1D15	C1D15	C1D15
No.	1	2	3	4	5	6	7	8	9	10	11	12
Time	pre-dose	2h	4h	6h	8h	24h	pre-dose	2h	4h	6h	8h	24h
Window(min)	-30	±10	±10	±30	±30	±60	-30	±10	±10	±30	±30	±60
Blood Sampling	2mL	2mL	2mL	2mL	2mL	2mL	2mL	2mL	2mL	2mL	2mL	2mL

7.2.2.2 Analytical method

Plasma samples were analyzed for HH2710 and metabolites using validated liquid chromatography-tandem mass spectrometry (LC/MS-MS) methods. Standard pharmacokinetic parameters were obtained using Phoenix WinNonlin 6.4 with a noncompartmental method. Relationship between dose and exposure was calculated using standard least-squares regression analysis.

7.2.3 Pharmacodynamics Biomarker Assessment

To confirm on-target and pathway inhibition by HH2710, RSK phosphorylation (pRSK/ total RSK) will be examined as a target biomarker in patient whole-blood sample pre-and post- HH2710 oral dosing in Phase I. Patients will undergo serial blood sampling for PD of HH2710 during cycle 1, and if applicable, during subsequent dosing cycles. This test will be done in sites that are capable of sample collection and processing for Pharmacodynamics.

Whole-blood sample will be collected on C1D1 and C1D15 (pre-dose, 4, and 24 hours post-dose) (time window is the same as related PK sampling time). Then peripheral blood mononuclear cells (PBMC) will be isolated and stimulated by PMA, followed by cell lysis and analyzed by ELISA for pRSK/RSK.

Biomarker sample collection information should be captured on sample collection CRF(s) and/or Central Laboratory paper requisition form(s).

Detailed instructions for the collection, handling, and shipping of samples for biomarker development are outlined in the HH2710-G101 Laboratory Manual.

7.2.4 Genetic Biomarkers Assessment

7.2.4.1 Genetic biomarker assessments in tumor samples during molecular screening

For the Phase I dose escalation, patients with regardless of MAPK pathway gene alteration status can participate clinical screening. If enrollment eligible patients' MAPK pathway gene status has been determined by local laboratory testing, the gene alteration status information from local test reports must be documented in the source files at the sites.

For Phase I dose expansion, local laboratory test results of MAPK pathway gene alteration status will be used to determine the eligibility of patient participating in clinical screening procedure. Each enrollment eligible patient must provide adequate archived and/or fresh FFPE tumor samples, which will be used for a MAPK pathway gene status determination at a Sponsor Designated Central Laboratory (only applicable in China sites). The MAPK pathway gene status from local labs should be confirmed and recorded by investigator, and must be documented in the source files at the sites (applicable in all sites).

For Phase II, patients with known MAPK pathway gene mutations from previous local laboratory testing can participate in clinical screening procedures. For enrolled patients with a pre-existing known MAPK pathway gene status, archived and/or fresh FFPE tumor samples must be provided for a confirmatory detection of MAPK pathway gene status by a Sponsor Designated Central Laboratory.

Alternatively, for patients without known MAPK pathway gene mutation, archived and/or freshly FFPE tumor biopsy samples must be provided for the MAPK pathway gene mutation pre-screening test by the Sponsor Designated Central Laboratory.

Patients must sign an informed consent form , to allow the collection of available test results of local laboratory and/or archived or fresh FFPE tumor tissue samples for the determination of the MAPK pathway gene alteration status at a Sponsor-Designated Central Laboratory .

In order to avoid false negatives in the use of tissue blocks that were archived prior to treatment failure, freshly collected or archived after a treatment failure, tissue samples can be collected from patients with previous standard treatments, chemotherapy intolerance, or patients who are clinically unsuitable for chemotherapy. The detailed instructions for the sample collection, handling and shipping are outlined in the (HH2710-G101 Laboratory Manual).

Table 7-4 Biomarker sample collection plan

Sample Type	Volume	Visit	Time point
Tumor samples			

Sample Type	Volume	Visit	Time point
Mandatory Either tumor block or a minimum of 10 slides from archival paraffin tumor tissue, or a freshformalin-fixed tumor biopsy	N/A	Phase Ib/II: before Day-28 and Day -28 –0 Requires patient's written consent on the Additional Biomarker ICF.	Anytime
Optional Fresh FFPE tumor biopsy tissue	N/A	Phase Ib/II: anytime when drug resistance occurred before Day-28 and Day -28 –0 Requires patient's written consent on the Additional Biomarker ICF.	Anytime
		Unscheduled if needed	Anytime
Blood samples			
Mandatory whole-blood samples (collection of whole-blood sample and PBMCs to measure marker “pRSK/RSK” to assess PD)	10 mL	C1D1	Pre-dose
	10 mL	C1D1	4 hours post-dose
	10 mL	C1D1	24 hours post-dose
	10 mL	C1D15	Pre-dose
	10 mL	C1D15	4 hours post-dose
	10 mL	C1D15	24 hours post-dose

8.1 Adverse events

8.1.1 Definition of Adverse Event (AE)

An adverse event is defined as the appearance of (or worsening of any pre-existing) undesirable sign(s), symptom(s), or medical condition(s) that occur after patient's signed informed consent has been obtained.

Abnormal laboratory values or test results occurring after informed consent constitute adverse events if they induce clinical signs or symptoms, require therapy, require changes in study medication(s) and other abnormalities are assessed by the investigator as clinical significance.

Progression of malignancy should be documented or recorded as a part of efficacy evaluation, but not be reported as an adverse event. Adverse events separate from the progression of malignancy (example, deep vein thrombosis at the time of progression) will be reported as per usual guidelines with proper attribution regarding relatedness to the drug.

8.1.2 Adverse Events Follow up and Reporting

Monitoring of adverse event begins when the patient's signed informed consent has been obtained and continued until the subject completes the safety follow-up.

Adverse events (including lab abnormalities that constitute AEs) should be described using a diagnosis whenever possible, rather than individual underlying signs and symptoms (e.g. anemia instead of low hemoglobin). When a clear diagnosis cannot be identified, each sign or symptom should be reported as a separate Adverse Event. When an abnormal laboratory or test result

corresponds to a sign/symptom of an already reported adverse event, it is not necessary to separately record the lab/test result as an additional adverse event.

The occurrence of adverse events should be sought by non-directive questioning during the screening process after taking the study treatment and at each visit during the study. Adverse events also may be detected when they are volunteered during the screening process or between visits, or through physical examination, laboratory test, or other assessments.

Once an adverse event is detected, it should be followed until its resolution/baseline or until its condition is judged to be stable, and assessment should be made at each visit (or more frequently, if necessary) of any changes in severity, the suspected relationship and action taken to the study treatment, the interventions required to treat it, and the outcome.

8.1.3 Assessment of Adverse Events

As far as possible, each adverse event should be evaluated to determine the following:

1. The severity grade (CTCAE Grade 1-5)

Adverse events will be assessed according to the Common Terminology Criteria for Adverse Events (CTCAE) version 5.0. If CTCAE grading does not exist for an adverse event, mild, moderate, severe, life-threatening and fatal (corresponding to Grades 1 - 5, respectively) will be used.

- Grade 1 -Mild; asymptomatic or mild symptoms; clinical or diagnostic observations only; intervention not indicated.
- Grade 2 -Moderate; minimal, local or noninvasive intervention indicated; limiting age-appropriate instrumental activities of daily living (ADL).
- Grade 3 -Severe or medically significant but not immediately life-threatening; hospitalization or prolongation of hospitalization indicated; disabling; limiting selfcare ADL.
- Grade 4 -Life-threatening consequences; urgent intervention indicated.
- Grade 5 -Death related to AE.

Note: A Grade 3 or 4 event (severe) as per CTCAE does not automatically indicate a SAE unless it meets the definition of serious as defined in Section 8.2.1.

2. Its duration (Start and end dates)

3. Its relationship to the study treatment.

Not related: There is alternative cause for the event which is better plausible to explain the event.

Related: there is a “reasonable possibility” that the drug caused the event.

To assess the relationship, carefully consider the following points:

- Time interval between AE and study drug administration, including time sequence and

reasonability

- Effects of other drugs or therapeutic interventions
- Effect of study indication or co-existent medical conditions
- If AE improved after study drug discontinuation or dose reduction
- If AE re-appeared upon study drug re-administration
- Mechanism of the study drug

4. Action taken with respect to study or investigational treatment due to adverse event (no change, dose decreased, dose interrupted, withdrawn, dose increased, not applicable)
5. All adverse events should be treated appropriately, whether medication or therapy was given should be recorded on the CRF. (no concomitant medication/non-drug therapy, concomitant medication/non-drug therapy)
6. Outcome (not recovered/not resolved, recovered/resolved, recovering/resolving, recovered/resolved with sequelae, fatal, unknown)
7. Whether it is serious, where a serious adverse event (SAE) is defined as in Section 8.2.1 .

8.2 Serious Adverse Event (SAE)

8.2.1 Definition of SAE

An adverse event is considered “serious” if it results in at least one of the following outcomes:

- Is fatal;
- Is life-threatening: refers to a reaction in which the patient was at risk of death at the time of the reaction; it does not refer to a reaction that hypothetically might have caused death if it were more severe;
- Requires inpatient hospitalization or prolongation of existing hospitalization;

Note that hospitalizations for the following reasons should not be reported as serious adverse events:

- Routine treatment or monitoring of the studied indication, not associated with any deterioration in condition;
- Elective or pre-planned treatment for a pre-existing condition that is unrelated to the indication under study and has not worsened since signing the informed consent;
- Social reasons and respite care in the absence of any deterioration in the patient’s general condition;
- Results in persistent or significant disability/incapacity;
- Constitutes a congenital anomaly/birth defect;
- Is medically significant, i.e., defined as an event that jeopardizes the patient or may require medical or surgical intervention to prevent one of the outcomes listed above;

Medical and scientific judgment should be exercised in deciding whether other situations should be considered serious reactions, such as important medical events that might not be immediately life threatening or result in death or hospitalization but might jeopardize the patient or might require intervention to prevent one of the other outcomes listed above. Examples of such events are intensive treatment in an emergency room or at home for allergic bronchospasm, blood dyscrasias or convulsions that do not result in hospitalization or development of dependency or abuse.

8.2.2 Serious Adverse Event Reporting

To ensure patient safety, every SAE, regardless of suspected causality, occurring after the patient has provided main informed consent and until completion of the safety follow-up must be reported to Haihe Pharmacovigilance team within 24 hours upon the awareness of its occurrence.

Any SAEs experienced after the safety follow-up period should be reported to Haihe Pharmacovigilance team only if the investigator suspects a causal relationship to the study treatment.

Information about all SAEs is collected and recorded on HaiHe Serious Adverse Event Report Form; all applicable sections of the form must be completed in order to provide a clinically thorough report. The investigator must assess and record the relationship of each SAE to the study treatment, complete the SAE Report Form in English, and send the completed, signed form by e-mail within 24 hours to the Haihe Pharmacovigilance Team. For SAE causing the death, the investigator should provide the Autopsy report or related medical reports if available.

The e-mail address and contact information of HaiHe Pharmacovigilance Team, are listed in the investigator folder provided to each site. The original copy of the SAE Report Form and acknowledgement of receipt must be kept with the case report form documentation at the study site.

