7.1.1 Molecular screening

For the Phase I does escalation, patients with regardless of MAPK pathway gene alteration status can participate clinical screening. If enrollment eligible patient's MAPK pathway gene status has been determined by local laboratory testing, the pre-existing test result should be submitted for documentation (applicable in all sites).

For the Phase I expansion stage, local laboratory test results of MAPK pathway gene alteration status will be used to determine the eligibility of patient participating in clinical screening procedure. Each enrollment eligible patient must provide adequate archival and/or fresh FFPE tumor samples, which will be used for a MAPK pathway gene status determination at a Sponsor Designated Central Laboratory (only applicable in China sites). The MAPK pathway gene status from local labs should be confirmed by investigator, and must be documented in the source files at the sites (applicable in all sites).

For the Phase II stage, patients with known MAPK pathway gene mutations from previous local laboratory testing can participate in clinical screening procedures. For enrolled patients with a pre-existing known MAPK pathway gene status, archival and/or fresh FFPE tumor samples must be provided for a confirmatory detection of MAPK pathway gene status by a Sponsor Designated Central Laboratory. The MAPK pathway gene status from local labs should be confirmed and recorded by investigator, and must be documented in the source files at the sites (applicable in all sites).

Alternatively, for patients without known MAPK pathway gene mutation, archival and/or fresh FFPE tumor biopsy samples must be provided for the MAPK pathway gene mutation pre-screening test by the Sponsor Designated Central Laboratory. In order to avoid false negatives in the use of tissue blocks that were archived prior to treatment failure, freshly collected or archived after a treatment failure, tissue samples can be collected from patients with previous standard treatments, chemotherapy intolerance, or patients who are clinically unsuitable for chemotherapy.

The detailed instructions for the sample collection, handling and shipping are outlined in the (HH2710-G101 Laboratory Manual).

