7.1.2 Screening examination

Written informed consent needs to be obtained from the patient prior to any screening procedures for main study. The patient will undergo screening procedures as part of screening visit, as indicated in the assessment schedule (

Name	Protocol Section	Screening period		Study treatment period							follow up period		
		0 molecular screening	1 Screening	Cycle 1 Day 1 through 21			Cycle 2 Day 22 through 42			Cycle 3-X 21d/cycle, visit on 1st day of every 2 cycles	End of treatment visit (EOT)/early discontinuation (Section 7.1.4)	Safety follow up	Progress Disease follow up
Day			-28 to -1	1 ± 0	8 ± 1	15 ± 1	22 ± 1	29 ± 3	36 ± 3	43 ± 3	N/A	+ 7	±7
molecular agent (Phase I and Phase II agent)	7.1.1	X											
consent	7.1.2		X										
exclusion criteria	5.2, 5.3		X										
detection	7.1.1	X1	X										
history/tumor treatment history	7.1.2.2		X2	X	X	X	X	X	X	X	X		
agnosis and history	7.1.2.2		X										
itant treatment	7.1.2.2		X	X	X	X	X	X	X	X	X	X	
raphy	7.1.2.2		X										
amination	7.2.1.1		X	X	X	X	X	X	X	X	X		
ight (cm)	7.2.1.3		X										
ight (kg)	7.2.1.3		X	X			X			X	X		
G	7.2.1.4		X	X	X	X	X	X	X	X	X		
signs	7.2.1.2		X	X6	X	X6	X	X	X	X	X		

		Screening period		Study treatment period							follow up period		
ame	Protocol Section	0 molecular screening			Cycle 1		Cycle 2		Cycle 3-X	End of treatment visit (EOT)/early discontinuation (Section 7.1.4)	Safety follow up	Progress Disease follow up	
			1 Screening	2 Baseline	3 Tx	4 Tx	5 Tx	6 Tx	7 Tx	8 Tx	Within 7 days of the last dose	30 days after the last dose.	Once every 6 weeks after the final dose
Day			-28 to -1	1 ± 0	8 ± 1	15 ± 1	22 ± 1	29 ± 3	36 ± 3	43 ± 3	N/A	+ 7	± 7
ogy exam	7.2.1.1		X	X	X	X				X	X		
cry test	7.2.1.5		X	X3			X4			X4	X4		
ispensed	6.6.3			X	X	X	X	X	X	X			
ministration	6.1.1			X5	X	X	X	X	X	X			
acokinetic ase I dose (on) ⁹	7.2.2.1			X		X	X			X			
acokinetic ase I dose (Phase II) ¹⁰	7.2.2.1			X		X							
lymnic ase I only)	7.2.3			X		X							
ssment by 1.1(CT etc)	7.2.5		X							X	X		X
iology	7.2.1.5		X	X7	X	X	X	X	X	X	X	X	
emistry			X	X7	X	X	X	X	X	X	X	X	
ysis			X	X7	If clinically indicated							X	
ation			X	X7		X							
unction			X	X8	X								
HIV test11	7.2.1.5		X										
gram (ECG)	7.2.1.7		X	X	X	X	X	X	X	X	X	X	
ogram or GA	7.2.1.6		X	At the investigator's discretion if there are signs or symptoms of cardiotoxicity.							X		

Name	Protocol Section	Screening period		Study treatment period							follow up period	

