7.1.2.1 Information to be collected on screening failure

A patient who signed an ICF but failed to be started on treatment for any reason will be considered a screen failure. Both, patients who signed a molecular pre-screening ICF but are considered ineligible after molecular pre-screening or fail to have a result report (i.e. no tumor in sample, poor

sample quality, assay failure), as well as patients, who are found not eligible after signing the main study ICF will be considered as screening failures and data will be handled in the same manner. The screening failure reason will be entered on the Screening Phase Disposition eCRF Page.

The demographic information, informed consent, and inclusion/exclusion pages must also be completed for Screening Failure patients. No other data will be entered into the clinical database for patients who are screening failures, unless the patient experienced a Serious Adverse Event during the molecular screening and/or screening period ([Section 8.2.2](#) for SAE reporting details).

Physical examinations should be symptom driven after the Screening Visit. Ophthalmological examinations will be performed by an ophthalmologist at screening, at each visit of C1, day 1 of C2, then day 1 of every 2 cycles.

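### Sections 7.1.2.1 and 8.2.2 give different start points for SAE reporting, so an SAE between the molecular screening consent and the main consent has no explicit 24-hour reporting duty

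*Protocol*

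**What the plan says.** The protocol uses two consents in sequence. Table 7-1 places the molecular screening consent (Phase I expansion and Phase II) at visit 0 and the main consent at visit 1. Section 7.1.2 ties the second to the main study: "Written informed consent needs to be obtained from the patient prior to any screening procedures for main study". Section 7.1.2.1 keeps the two forms apart when it defines screening failures, who include "patients who signed a molecular pre-screening ICF but are considered ineligible after molecular pre-screening".

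For screening failures, 7.1.2.1 limits what is entered in the database, "unless the patient experienced a Serious Adverse Event during the molecular screening and/or screening period", and cites 8.2.2 for reporting details. Section 8.2.2 applies the 24-hour duty to "every SAE, regardless of suspected causality, occurring after the patient has provided main informed consent and until completion of the safety follow-up". Section 8.1.2 says AE monitoring begins when the patient's "signed informed consent has been obtained and continued until the subject completes the safety follow-up"; neither it nor the AE definition in 8.1.1 says which consent is meant.

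On procedures before the main consent, section 7.1.1 says that in Phase II, for patients without a known mutation, "archival and/or fresh FFPE tumor biopsy samples must be provided for the MAPK pathway gene mutation pre-screening test". Section 7.2.4.1 repeats this.

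**The concern.** The one section that sets a deadline and a recipient for SAE reports opens its window at the main consent. Another section sends it events from before that point. A site that follows 7.1.2.1 would report a serious complication of a pre-screening procedure, while a site that follows the first sentence of 8.2.2 could conclude that no expedited report is due. Both would be following the protocol.

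What is at stake is prompt notice of harm from a procedure done for the study in people who may never receive study drug. A fresh tumour biopsy is the clearest example, because it is invasive and can come before the main consent.

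**Working it through.** No arithmetic applies. The check sets the start points side by side.

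| Place | What it governs | Start point | Consent named? |
|---|---|---|---|
| 7.1.2.1 | Database entry of SAEs in screening failures; refers to 8.2.2 | Molecular screening or screening period | Distinguishes molecular and main forms |
| 8.1.1 | Definition of an AE | Signed consent | No |
| 8.1.2 | AE monitoring | Signed consent | No |
| 8.2.2, first paragraph | 24-hour SAE report | Main consent | Yes, main |
| 8.2.2, third paragraph | Use and sending of the SAE form | None given; speaks of all SAEs | No |
| Table 7-1, AE row | Visits at which AEs are collected | Appears to begin at visit 1, with visit 0 blank | Not stated |

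Four kinds of patient show where the rules part.

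1. *Unknown mutation status, Phase II, fresh biopsy, fails molecular screening.* The patient signs the molecular form only. An SAE after the biopsy is to be entered in the database under 7.1.2.1. The first paragraph of 8.2.2 does not reach it, because the main consent is never given.
2. *Same patient, but passes and signs the main form later.* The SAE came before the main consent, so it is still outside the first paragraph of 8.2.2. The screening-failure exception in 7.1.2.1 no longer applies to this patient. Section 7.2.1.1 files findings present before consent as medical history and new ones as AEs, again without saying which consent.
3. *Unknown status, archival tissue supplied.* The start-point mismatch is the same, but no new invasive procedure precedes the main consent.
4. *Mutation already known locally, Phase II.* The patient goes straight to clinical screening, and the confirmatory sample is asked of enrolled patients. The gap has little practical content here.

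Two further points bear on the repair.

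- **End of the window.** The duty in 8.2.2 runs to the end of safety follow-up, which 7.1.5.1 sets at 30 days after the last dose. A screening failure has no last dose. Moving only the start point would leave the window without an end for patient 1.
- **Causality.** Sections 8.1.3 and 8.2.2 ask for relationship to study treatment only. A patient who has not been dosed can have no event related to treatment, and nothing asks whether a study procedure caused it. The later provision in 8.2.2, for events after safety follow-up, also depends on suspected relationship to treatment.

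Table 7-4 places tissue collection partly before Day -28 and under an Additional Biomarker consent. Its relation to the molecular pre-screening form is not explained, so the protocol has three consent names to reconcile.

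**The case against.** The strongest reply is that capture is already provided for. Section 7.1.2.1 makes an express exception so that these SAEs enter the database. The third paragraph of 8.2.2 speaks of all SAEs, without the main-consent limit, and has the form sent within 24 hours. Section 11.3 requires consent before any study-specific procedure, which supports reading the unnamed consent in 8.1.1 and 8.1.2 as the first one signed. A sensible site could combine these and report.

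Much of this stands, and it rules out several stronger readings.

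- *A reader might infer that such SAEs are never reported.* The documents do not support that, for the reasons just given. The defect is an unclear and conflicting start to expedited reporting.
- *A reader might infer that the study requires a pre-screening biopsy.* It requires tissue. Sections 7.1.1 and 7.2.4.1 and Table 7-4 accept archival material, and central pre-screening of patients with unknown status is described for Phase II only.
- *A reader might try to size the problem* by dividing Cohort 2's 36 patients by the 2-4% BRAF prevalence in section 1.1. That would count patients pre-screened, not biopsied. It also needs an assumed share found by central testing, and it ignores both the NRAS patients and the restriction to listed BRAF sites.
- *A reader might blame this wording for a lack of committee review.* Sections 4.2 and 10.5.1 tie the safety reviews to patients who received treatment. The wording of 8.2.2 neither causes nor cures that.

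It is also fair to say that SAP section 7 reports the programme stopped and the study terminated early, and nothing in the documents shows that Phase II opened. This lowers the urgency.

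The reply does not remove the conflict. The first paragraph of 8.2.2 says which SAEs carry the duty and specifies the main consent, a term that 7.1.2.1 uses in contrast to the molecular form. A protocol that needs its third paragraph to override its first is not clear enough for a 24-hour duty.

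**Conclusion.** The conflict between 7.1.2.1 and 8.2.2 is real, and 8.1.1 and 8.1.2 do not resolve it. On a literal reading, an SAE between the molecular consent and the main consent has no explicit 24-hour duty to pharmacovigilance, although the protocol expects it to be captured.

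The size cannot be given as a number: the documents state neither how many patients would be pre-screened nor how many would need a fresh biopsy. The clearest exposure is Phase II patients of unknown mutation status without usable archival tissue. Table 7-1 also asks for molecular consent in Phase I expansion, but eligibility there rests on local results.

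The effect is on the protection of participants and on consistency between sites. The SAP tabulates only treatment-emergent AEs in dosed patients (sections 6.2 and 8.8.1.1), so its safety tables do not change.

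The conclusion rests on taking the word main in 8.2.2 at its ordinary meaning, and on the AE row of Table 7-1 beginning at visit 1, as it appears to. The first alone is enough for the conflict. It is a modest point, but worth correcting because it concerns a safety duty and costs little.

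**What to change.** Reconcile 7.1.2.1, 8.1.1, 8.1.2, 8.2.2 and the AE row of Table 7-1 as follows.

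- **Start.** Name the consent that starts AE collection in 8.1.1 and 8.1.2. In 8.2.2, extend the 24-hour duty to SAEs after the molecular screening consent. If burden is a worry, limit the period before the main consent to SAEs related to protocol-required procedures. Say whether the Additional Biomarker form in Table 7-4 is the same document as the molecular form.
- **Causality.** Add relationship to study procedures to the assessment in 8.1.3 and 8.2.2. The procedure-related limit cannot work without it.
- **End.** State when reporting stops for screen failures who are never dosed, since the present end point depends on a last dose.
- **Schedule.** Mark SAE collection in the molecular screening column of Table 7-1.

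The cost is a wording amendment, a causality item on the SAE form, and a few extra SAE forms for pre-screened patients. No dose, eligibility rule or planned analysis changes. Because the study has stopped, the sponsor can instead check whether any SAE occurred between the two consents and, if so, whether it reached pharmacovigilance, and carry the corrected wording into later protocols that use a two-step consent.
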